1.2.3.1. Safety

The safety, efficacy, and PK of elranatamab were initially evaluated in Phase 1 study (C1071001) as monotherapy (IV and SC) or in combination with lenalidomide or pomalidomide.

As of the 22 June 2022 data cutoff date, 101 participants have been enrolled in the study as follows: 23 in Part 1 IV dose escalation, 30 in Part 1 SC dose escalation, 20 in Part 1.1 SC priming dose cohorts, 15 in Part 2A: SC dose dose expansion, 4 in Part 1C: elranatamab + lenalidomide and 9 in Part 1D: elranatamab + pomalidomide. In Part 1.1, to mitigate the risk of CRS and ICANS, participants received a priming dose of 600 µg/kg elranatamab (equivalent to 44 mg) on Day 1 prior to the first full dose of 1000 µg/kg (equivalent to 76 mg) on Day 8. In Part 2A, in addition to the priming dose of elranatamab, participants received pre-medication with dexamethasone, acetaminophen and diphenhydramine prior to the first 2 doses, priming dose and first full dose respectively.

Based on the data from this study, 76 mg QW administered SC was selected as the RP2D of elranatamab for future studies. This section will focus on safety data from participants who received elranatamab monotherapy at the full 1000 µg/kg or 76 mg [QW or Q2W] dosing regimen (N=41) regardless of priming dose or premedication.

In the 41 participants who received elranatamab monotherapy at the full 1000 µg/kg or 76 mg [QW or Q2W] dosing regimen, the most common all causality TEAEs (frequency $\geq 20\%$) were CRS (87.8%), neutropenia (78.0%), anemia (63.4%), ISR (56.1%), thrombocytopenia and fatigue (each 48.8%), diarrhea, hypophosphatemia and lymphopenia (each 39.0%), decreased appetite and dry skin (each 36.6%), back pain (34.1%), nausea and hypomagnesaemia (each 31.7%), AST increased and leukopenia (each 26.8%), ALT increased, fall, hypokalemia, pyrexia, vomiting, pain in extremity and weight decreased (each 24.4%), arthralgia, cough, dyspnoea, headache and pneumonia (each 22.0%).

For additional information, refer to the single reference safety document (SRSD), which for this study is the Investigator's Brochure.

PF-06863135
C1071001
Final Protocol Amendment 9, 28 March 2023

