3.1.4. Criteria for Dose Escalation/De-Escalation

The study has been designed to establish the MTD/MAD defined as the dose that yields approximately 25% probability of DLT and considers equivalent doses that yield probability of DLT in the interval (Equivalence Interval) 20% to 30%.

All dose escalation/de-escalations will be guided by the mTPI design and therefore 2-4 patients will be enrolled in each cohort (see [Section 3.1 Study Overview](#)).

The potential dose levels to be evaluated for Part 1 IV administration are listed in [Table 2](#). The potential dose levels to be evaluated for Part 1 SC administration are listed in [Table 3](#).

Dose escalation for Part 1 IV and SC will start at dose level 1 for each ([Table 2](#) and [Table 3](#)).

In Part 1, for both IV and SC administration, the maximum dose increase will be approximately 3 fold if no DLTs are observed; per mTPI, intermediate or higher doses may be evaluated based on clinical findings.

PF-06863135
C1071001
Final Protocol Amendment 9, 28 March 2023

Table 2. Table of Potential Dose Levels in Part 1 IV Administration

| Dose level | Dose (μ g/kg) |
|------------|-----------------------|
| 1 | 0.1 |
| 2 | 0.3 |
| 3 | 1.0 |
| 4 | 3.0 |
| 5 | 10.0 |
| 6 | 30.0 |
| 7 | 50.0 |

Table 3. Table of Potential Dose Levels in Part 1 SC Administration

| Dose level | Dose (μ g/kg) |
|------------|-----------------------|
| 0 | 50 |
| 1 | 80 |
| 2 | 130 |
| 3 | 215 |
| 4 | 360 |
| 5 | 600 |
| 6 | 1000 |

In Part 1.1, the starting maintenance dose will be no more than 2-fold above the priming dose established from Part 1. Maximum maintenance dose increases will be 2-fold (100%).

Q2W dosing would be evaluated upon reaching MTD/MAD. Cycles for Q2W dosing would be 4 weeks rather than the 3 weeks with Q1W dosing. Both Q1W and Q2W dosing may be considered for Part 2A expansion from Part 1.

Once the first DLT is observed, the maximum increase would increase no more than 2-fold up to 3 μ g/kg, and no more than 67% beyond 3 μ g/kg.

Parts 1C, and 1D will combine escalating doses of PF-06863135 starting at the monotherapy MTD-1/MAD-1 or RP2D (whichever is lower) dose level and increasing to the monotherapy RP2D/MTD, if applicable, in combination with a standard dose of lenalidomide or pomalidomide, respectively. De-escalation of PF-06863135 to a lower dose level may occur if necessary.

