Details for PF-06863135 injections are provided in the current PF-06863135 IP Manual. The dose level will be assigned by the sponsor (see [Section 5.1 Allocation to Treatment](#)). For monotherapy Part 1, all patients should be weighed within 72 hours prior to Day 1 of each cycle to ensure they did not experience either a weight loss or gain >10% from the prior weight used to calculate the amount of PF-06863135 required for dose preparation. If the patient experienced either a weight loss or gain >10% compared to the prior weight used to calculate the initial dose or dose in the previous cycle, the amount of PF-06863135 required for preparation and administration for the current cycle must be recalculated using this most recent weight obtained. Should the institutional policy be such that the dose is required to be calculated if a patient experiences a weight gain of <10%, this will be allowed. Fixed-dosing approach will be applied in dose-finding for combination and also in all expansion parts of the study (See [Section 1.2.9.4](#)).

Each patient may receive PF-06863135 until disease progression, unacceptable toxicity, withdrawal of consent, patient no longer willing to participate in trial, or study termination. If a patient has received treatment with Q1W PF-06863135 for at least 6 months, and disease assessments have remained stable over at least 2 months, consideration may be given to increasing dose intervals from weekly to every 2 weeks or once per cycle (only CXD1 dosing and activities applicable) after consultation with sponsor. Cycles would remain the same length with any skipped weekly doses noted. If the patient subsequently begins to have increase of disease burden, dose intervals should return to weekly dosing.

For Parts 1C, 1D, 1E and Part 2 dose expansion: PF-06863135 will be administered as described for monotherapy PF-06863135, and each cycle will be 4 weeks in duration. On C1D1 for all patients and C0D1 for patients receiving a priming dose, PF-06863135 will be administered on an inpatient basis. On all other days, PF-06863135 will be administered on an outpatient basis.

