5.5.2. Dose Delays

Re-treatment following treatment interruption for treatment-related toxicity or at the start of any new cycle should not occur until all of the following parameters have been met:

- ANC $\geq 1,000/\text{mm}^3$ for PF-06863135, dexamethasone, and lenalidomide; $\geq 500/\text{mm}^3$ for pomalidomide;
- Platelets count $\geq 25,000/\text{mm}^3$ for PF-06863135 and dexamethasone; $\geq 30,000/\text{mm}^3$ for lenalidomide; $\geq 50,000/\text{mm}^3$ for pomalidomide;
- Non-hematologic toxicities have returned to baseline or Grade ≤ 1 severity (or, at the investigator's discretion, Grade ≤ 2 if not considered a safety risk for the patient).
- Recovery of treatment-emergent peripheral neuropathy to Grade ≤ 1 severity.

If a treatment delay results from worsening of hematologic or biochemical parameters, the frequency of relevant blood tests should be increased as clinically indicated.

If these conditions are met within 3 weeks of treatment interruption or cycle delay, study treatment may be resumed. Refer to the Dose Reductions Section 5.5.3 for adverse events requiring dose reduction at the time of treatment resumption.

If these conditions are not met, treatment resumption must be delayed up to a maximum of 3 weeks. If patients require discontinuation of study treatment for more than 42 days of Day 1 of the current cycle, then study treatment should be permanently discontinued, unless the investigator's benefit/risk assessment suggests otherwise after discussion with the Sponsor's medical monitor.

If a treatment interruption continues beyond the last day of the current cycle, then the day when treatment is restarted will be counted as Day 1 of the next cycle.

Recommended guidelines for dose delays of PF-06863135 for participants who have active [confirmed (positive by regulatory authority-approved test) or presumed (test pending/clinical suspicion)] SARS-CoV2 infection can be found in [Appendix 10](#).

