8.2.3.5. Treatment Administration/Compliance

Listings and tables by dose level will be provided. Day 1 of a cycle is the date of first dose within that cycle. Each cycle is a 3-week period for Part 1, or 4-week period for Parts 1.1 1C, 1D, 1E, 2A, 2C, 2D, or 2E except cycle 0 for priming dose. The safety analysis set will be used.

The following will be summarized by subject for each dose level:

- Number of subjects per dose level;
- Median and range of number of cycles started per subject;
- Number (%) of subjects starting a cycle (1, 2, 3...);
- Number (%) of subjects with cycle delays;
- Number (%) of dose interruptions (include both known and unknown dates);
- Number (%) of subjects with dose reductions;
- Number (%) of each reason (AE vs. Other) for cycle delays, dose interruptions and dose reductions;
- Time on treatment (median, range).

The following will be summarized by cycle received for each dose level:

- Total number of cycles started;
- Number of cycles started per subject (median, range);

The following will be summarized for cumulative dose by dose level and cycle: Summary statistics (mean, median, standard deviation and range) of cumulative dose and percent of starting dose (compared to Day 1 dose of each cycle).

Listings by subject (ordered by dose level): start date and stop date of each dosing period within each cycle (including records with 0 mg), administered total daily dose for each period, any missed doses with unknown dates (Y/N), number of missed doses with unknown dates, reason for any dosing changes. Listings by subject and each cycle (ordered by dose level): cycle length, total planned dose, administered total dose, percentage of planned dose, dose delay (yes/no), dose reduction (yes/no), and dose interruption (yes/no).

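### The 42-day stopping limit in Protocol 5.5.2 fits 21-day cycles only: in 28-day cycles, a new cycle delayed by 15 to 21 days gets two opposite default instructions

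*Protocol*

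**What the plan says.** Protocol 5.5.2 is a single rule for every part of the study. It sets recovery criteria for restarting after an interruption or at the start of a new cycle, and then says: "If these conditions are met within 3 weeks of treatment interruption or cycle delay, study treatment may be resumed". The next paragraph deals with patients who have not met the criteria and caps the delay at 3 weeks. It then adds that if treatment must be off "for more than 42 days of Day 1 of the current cycle, then study treatment should be permanently discontinued", with an exception where the investigator's benefit/risk assessment favours continuing after discussion with the sponsor's medical monitor.

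The section also says which cycle is current during a hold. If an interruption runs past the end of a cycle, "then the day when treatment is restarted will be counted as Day 1 of the next cycle". Until the restart, the clock therefore still runs from Day 1 of the cycle last started.

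Cycle length differs by cohort. Weekly Part 1 monotherapy without priming uses 3-week cycles. For Parts 1C, 1D, 1E and Part 2, Protocol 5.4.2 says "each cycle will be 4 weeks in duration". For Q2W cohorts, Protocol 3.1.4 says "Cycles for Q2W dosing would be 4 weeks rather than the 3 weeks with Q1W dosing". SAP 8.2.3.5 agrees and adds Part 1.1: "Each cycle is a 3-week period for Part 1, or 4-week period for Parts 1.1 1C, 1D, 1E, 2A, 2C, 2D, or 2E". Neither 5.5.2 nor 5.5.3 gives a version of the 42-day limit for 28-day cycles.

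**The concern.** Forty-two days is exactly one 21-day cycle plus a 3-week delay. The same number has been kept for cohorts with 28-day cycles, where one cycle plus a 3-week delay is longer. A late start of a 28-day cycle can then be permitted by one sentence and stopped by default under the other.

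This is a treatment-stopping rule on the schedule used at the recommended Phase 2 dose. Under one sentence the investigator may restart alone. Under the other, stopping is the default and a restart needs a discussion with the medical monitor. A recovered patient, possibly in response, could be taken off treatment although the 3-week allowance covers the delay. Another could be restarted past the limit without the required discussion.

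A stop can also reach the analysis. SAP Table 4 censors PFS when treatment is discontinued for toxicity, SAP 8.2.2.6 applies those rules to duration of response, and duration of response is a primary endpoint in Part 2.

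**Working it through.** **Inputs**
- Restart allowance and maximum delay: 3 weeks = 21 days (Protocol 5.5.2).
- Default stop: more than 42 days, counted from Day 1 of the current cycle (Protocol 5.5.2).
- Cycle length L: 21 days for weekly Part 1 without priming. It is 28 days for Parts 1.1, 1C, 1D, 1E, Part 1 SC Q2W and Part 2 (Protocol 3.1.4 and 5.4.2; SAP 8.2.3.5).

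**Formula**

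Days elapsed since Day 1 when a hold of d days ends = (day of first withheld dose − 1) + d. For a delayed new cycle the first withheld dose falls on Day L + 1, so elapsed days = L + d. A conflict exists when d is at most 21 and the elapsed days exceed 42.

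**The plan's own figure**

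With L = 21 and d = 21, elapsed days = 21 + 21 = 42. That is not more than 42, so the two limits meet exactly.

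**End of a full 21-day hold, by first withheld dose**

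| First withheld dose | 21-day cycle | 28-day cycle |
|---|---|---|
| Day 8 | 7 + 21 = 28 | 7 + 21 = 28 |
| Day 15 | 14 + 21 = 35 | 14 + 21 = 35 |
| Day 22 | 21 + 21 = 42 (next Day 1) | 21 + 21 = 42 |
| Day 29 | not applicable | 28 + 21 = **49** (next Day 1) |

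Only the delayed start of a 28-day cycle passes 42.

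**Width of the conflict**

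In a 28-day cycle, d = 14 gives 42 and is allowed. From d = 15 (43 days) to d = 21 (49 days) both instructions apply. Restart would fall on calendar Days 44 to 50. That is 7 of the 21 permitted delay lengths; it is a share of days, not of patients.

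**Counting convention**

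If Day 1 is numbered 1 and day numbers are compared with 42, the conflicting range becomes 14 to 21 days. That count also puts a 21-day delay of a 21-day cycle over the limit (21 + 1 + 21 = 43). Elapsed days is the count under which the plan's two limits agree.

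**Where it can arise**

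The first withheld dose must be the next Day 1. That is 1 of 4 dose days on weekly dosing and 1 of 2 on Q2W. Patients stable on weekly dosing for at least 6 months may also move to dosing "once per cycle (only CXD1 dosing and activities applicable"), and every hold on that regimen is a delayed cycle start.

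**Cohorts exposed**

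At the 22 June 2022 cutoff Protocol 1.2.3.1 lists "20 in Part 1.1 SC priming dose cohorts, 15 in Part 2A", 4 in Part 1C and 9 in Part 1D: 20 + 15 + 4 + 9 = 48. With 23 in Part 1 IV and 30 in Part 1 SC the total is 101, and 48/101 = 47.5%. Any Part 1 SC Q2W patients would add to the 48 but are not listed separately. None are listed in Parts 1E, 2C, 2D or 2E.

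**The case against.** The best counter-argument is structural. The permission to restart covers patients who meet the criteria within 3 weeks, while the 42-day sentence sits in the paragraph for those who do not. On that reading a patient who recovers on day 15 to 21 of a delay never reaches the stop rule. Nor does the reading empty the rule: for holds that begin on Day 8 or Day 15, 3 weeks end at 28 or 35 days, and 42 days still sets an outer bound 14 or 7 days later. That much is right. It does not remove the conflict. A patient still unrecovered on day 15 of a delayed 28-day cycle is in the unrecovered branch and already at 43 days. The default stop applies while the same section still allows until day 21 to recover. The 42-day sentence itself carries no condition on recovery.

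A second reading takes 42 days as time off drug, which a 21-day delay cannot reach. It disregards the stated reference to Day 1. The figure of more than 42 days in Protocol 5.5.3 is the duration of a myelosuppression DLT, a different clock. The sentence is loosely worded, however, and that is a further reason to clarify it.

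Third, a permission and a default with an override can be followed together by calling the medical monitor between 43 and 49 days. The practical difference may be one conversation. But whether that conversation is required is exactly what the text leaves open.

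Fourth, oversight is not proven. The amendment log ties the 42 days to Day 1 in Amendment 3 and brings in the 4-week cycle in Amendment 4. It also shows 5.5.2 revised again in Amendments 5, 7 and 8. Retaining 42 days could have been deliberate, so the intent is unknown.

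**Conclusion.** The concern holds. Protocol 5.5.2 gives opposite default instructions for a new 28-day cycle delayed by 15 to 21 days, a 7-day window between 42 and 49 days after Day 1. There is no conflict in 21-day cycles, or in 28-day cycles when the hold begins on Day 8, 15 or 22.

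This rests on two readings: that the 42 days run as elapsed days from Day 1, and that the current cycle is the one last started. Both follow from the section's own wording, and the exact match at 21 + 21 supports the first.

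The practical reach is modest. Enrolment is complete, the 48 of 101 counts patients enrolled rather than patients still treated, and no hold in the 15-to-21-day window is documented. Sample size, power and error rates are untouched. It is still worth correcting, because a stated stopping threshold does not fit the cycle length of the cohorts it governs.

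**What to change.** In Protocol 5.5.2, replace the fixed 42 days with cycle length + 21 days from Day 1 of the current cycle: 42 days for 21-day cycles and 49 days for 28-day cycles. Leave the medical-monitor override as it is. With that limit no permitted delay exceeds the stop.

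If 42 days is intended for all cycle lengths, say so, and state that in 28-day cycles the start of a cycle may be delayed by at most 42 − 28 = 14 days without medical-monitor agreement.

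Either version is one sentence in a clarification letter or the next amendment. It needs no extra visits, patients or data.

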5.5.3. Dose Reductions

Following dosing interruption or cycle delay due to toxicity, the PF-06863135 dose may need to be reduced when treatment is resumed.

No specific dose adjustments for PF-06863135 are recommended for Grade 1/2 treatment-related toxicity. However, investigators should always manage their patients according to their medical judgment based on the particular clinical circumstances.

Patients experiencing recurrent and intolerable Grade 2 toxicity may resume dosing at the next lower dose level of PF-06863135 once recovery to Grade ≤ 1 or baseline is achieved.

PF-06863135

C1071001

Final Protocol Amendment 9, 28 March 2023

Dose reduction of PF-06863135 by 1 and, if needed, 2 dose levels will be allowed depending on the type and severity of toxicity encountered. Patients enrolled in the first (0.1 µg/kg) cohort will be allowed 1 dose reduction if required. Patients requiring more than 2 dose reductions (or 1 dose reduction for the first cohort) will be discontinued from the treatment and entered into the follow-up phase, unless otherwise agreed between the investigator and the sponsor. If dose reduction of PF-06863135 is needed for any patient who receives fixed doses of PF-06863135 (Parts 1C, 1D, 1E, 2A, 2C, 2D, 2E), the next dose level of PF-06863135 will be 25% lower than the current dose level (eg, from 32 mg to 24 mg, or from 24 mg to 16 mg). All dose modifications/adjustments must be clearly documented in the patient's source notes and case report form (CRF).

Once a dose has been reduced for a given patient, all subsequent cycles should be administered at that dose level, unless further dose reduction is required. Intrapatient dose re-escalation is not allowed.

Patients experiencing a DLT may resume dosing at the next lower dose level (if applicable) once adequate recovery is achieved. Patients experiencing a DLT of prolonged myelosuppression (>42 days) may not resume treatment even if adequate recovery is achieved. No dose reductions are planned for patients experiencing toxicities other than those listed as DLTs. However, patients experiencing recurrent and intolerable Grade 2 toxicity may resume dosing at the next lower dose level once recovery to Grade ≤1 or baseline is achieved. Patients whose hematologic indices improve prior to meeting the criteria for prolonged myelosuppression >42 days may resume dosing at the next lower dose level or permanently discontinue from treatment at the discretion of the investigator.

Recommended dose reductions for PF-06863135 are described in Table 5.

Table 5. Dose Modifications for PF-06863135 Product-Related Toxicity and for Peripheral Sensory or Motor Neuropathy***

| Toxicity | Grade 1 | Grade 2 | Grade 3 | Grade 4 |
|--|----------------------------------|----------------------------------|--|--|
| Non-hematologic (excluding peripheral neuropathy-see below) | Continue at the same dose level. | Continue at the same dose level. | Withhold dose until toxicity is Grade ≤1, or has returned to baseline, then reduce the dose by 1 level.* | Permanently discontinue.* |
| Hematologic except for lymphopenia, which is expected as part of PF-06863135 mechanism of action | Continue at the same dose level. | Continue at the same dose level. | Withhold dose until toxicity is Grade ≤2, or has returned to baseline, then resume treatment at the same dose level.** If toxicity reoccurs, dosing may be reduced by 1 dose level. If | Withhold dose until toxicity is Grade ≤2, or has returned to baseline, then reduce the dose by 1 level and resume treatment.** If toxicity reoccurs despite dose reduction, dosing may be reduced by |

PF-06863135
C1071001
Final Protocol Amendment 9, 28 March 2023

Table 5. Dose Modifications for PF-06863135 Product-Related Toxicity and for Peripheral Sensory or Motor Neuropathy***

| Toxicity | Grade 1 | Grade 2 | Grade 3 | Grade 4 |
|--|--|---|--|--|
| | | | 
toxicity reoccurs after a maximum of 2 dose level reductions (1 for patients in first cohort), patient may be permanently discontinued from treatment.
 
For platelets, withhold dose if toxicity $\leq 25,000 \text{ mm}^3$ and re-start when platelets have returned to $\geq 25,000 \text{ mm}^3$ or baseline
 | 1 more dose level. If toxicity reoccurs, patient may be permanently discontinued from treatment. |
| Peripheral sensory or motor neuropathy (all causality) See Section 8.4.4 for recommended work-up. | 
Continue at the same dose level.
 
Continue to monitor the participant for signs of worsening neuropathy
 | 
Withhold dose until resolution to Grade ≤ 1, then resume at a reduced dose level.
 
Continue to monitor the participants for signs of worsening neuropathy.
 
If Grade ≥ 2 neuropathy reoccurs, permanently discontinue elranatamab.
 | Permanently discontinue elranatamab. | Permanently discontinue elranatamab |

* Nausea, vomiting, or diarrhea must persist at Grade 3 or 4 despite maximal medical therapy to require dose modification.

** Cycle will not be extended to cover for the missing doses.

*** Dose reductions for lenalidomide should also follow the recommendations in this table.

Doses may be held as needed until toxicity resolution. Appropriate follow-up assessments should be done until adequate recovery occurs as assessed by the investigator.

Dose modifications for lenalidomide (ie, for neutropenia, thrombocytopenia, renal impairment, grade 3 or 4 toxicities judged to be related to lenalidomide) per manufacturer's guidelines is permitted. Please see, [Table 7](#) and [Table 8](#) hematologic toxicities and renal impairment for dose modifications. Please consult the Revlimid® US package Insert (USPI)

PF-06863135

C1071001

Final Protocol Amendment 9, 28 March 2023

for further details.³⁰ For Europe, please consult the Revlimid® Summary of Product Characteristics (SPC) for further details.³¹ For Canada, please consult the Revlimid® Product Monograph for further details.³²

Table 6. Lenalidomide Dose Adjustment for Thrombocytopenia

| Platelet Count | Recommended Course of Action |
|---|--|
| 
 When count first falls to <30,000 mcL. When count returns to $\geq 30,000$ mcL. | 
 Interrupt lenalidomide treatment, follow complete blood count (CBC) weekly. Resume lenalidomide at 10 mg. |
| 
 For each subsequent drop in count to <30,000 mcL. When count returns to $\geq 30,000$ mcL. | 
 Interrupt lenalidomide treatment. Resume lenalidomide at the next lower dose level (5 mg) once daily. Do not decrease dose below 5 mg once daily. |

Table 7. Lenalidomide Dose Adjustment for Neutropenia

| Neutrophil Count | Recommended Course of Action |
|---|---|
| 
 When count first falls to <1,000/mcL. When count returns to $\geq 1,000$/mcL and neutropenia is the only observed toxicity. When count returns to $\geq 1,000$/mcL and other toxicity is observed. | 
 Interrupt lenalidomide treatment, start G-CSF treatment, follow CBC weekly. Resume lenalidomide at 15 mg once daily. Resume lenalidomide at 10 mg once daily. |
| 
 For each subsequent drop in count to <1,000/mcL. When count returns to $\geq 1,000$/mcL. | 
 Interrupt lenalidomide treatment. Resume lenalidomide at the next lower dose level (10 mg or 5 mg) once daily. Do not decrease dose below 5 mg once daily. |

PF-06863135

C1071001

Final Protocol Amendment 9, 28 March 2023

Table 8. Lenalidomide Dose Adjustment for Renal Impairment

| Category | Renal Function | Dose |
|---------------------------|---|---|
| Moderate renal impairment | CrCl ^a 30-60 mL/min | 10 mg every once daily |
| Severe renal impairment | CrCl ^a <30 mL/min (not requiring dialysis) | 15 mg every other day |
| End-stage renal disease | CrCl ^a <30 mL/min (requiring dialysis) | 5 mg once daily. On dialysis days, administer the dose after dialysis |

Key: CrCl = creatinine clearance.

a Estimated by creatinine clearance as calculated by the Cockcroft-Gault equation.

For recommended lenalidomide dose modifications for peripheral neuropathy (all causality), refer to [Table 5](#).

Dose modifications for pomalidomide (ie, for neutropenia, thrombocytopenia, strong CYP1A2 inhibitors, severe renal impairment, or hepatic impairment) per manufacturer's guidelines is permitted. Please see Table 9 hematologic toxicities for dose modifications. Please consult the Pomalyst® US package Insert (USPI) for further details.³⁴ For Europe, please consult the Innovid® Summary of Product Characteristics (SPC) for further details.³⁵ For Canada, please consult the Pomalyst® Product Monograph for further details.³⁶

Table 9. Dose Modification Instructions for Pomalidomide for Hematologic Toxicities

| Interruption/resumption threshold | Dose Modification |
|--|--|
| Neutropenia | |
| ANC* <500 per mcL or Febrile neutropenia (fever \geq to 38.5°C and ANC <1,000 per mcL) ANC return to \geq 500/mcL | Interrupt pomalidomide treatment, follow CBC weekly. Resume pomalidomide at 3 mg daily. |
| For each subsequent drop <500/mcL Return to \geq 500/mcL | Interrupt pomalidomide treatment. Resume pomalidomide at 1 mg less than the previous dose |
| Thrombocytopenia | |
| Platelets <25,000/mcL Platelets return to $>50,000/\text{mcL}$ | Interrupt pomalidomide treatment, follow CBC weekly. Resume pomalidomide treatment at 3 mg daily. |
| For each subsequent drop <25,000/mcL Return to more than or equal to 50,000/mcL | Interrupt pomalidomide treatment. Resume pomalidomide at 1 mg less than previous dose. |

*Note: ANC = Absolute Neutrophil Count

For other Grade 3 or 4 toxicities (except as noted below), hold treatment and restart treatment at 1 mg less than the previous dose when toxicity has resolved to less than or equal to Grade 2 at the physician's discretion. For anaphylactic reactions, angioedema, progressive

PF-06863135

C1071001

Final Protocol Amendment 9, 28 March 2023

multifocal leukoencephalopathy (PML), or rash (Grade 4 or blistering), pomalidomide should be permanently discontinued.

To initiate a new cycle of pomalidomide, the neutrophil count must be at least 500 per mcL, the platelet count must be at least 50,000 per mcL. If toxicities occur after dose reductions to 1 mg, then discontinue pomalidomide.

- Dosage Adjustment for Strong CYP1A2 Inhibitors:
 - Avoid concomitant use of pomalidomide with strong inhibitors of CYP1A2. Consider alternative treatments. If a strong CYP1A2 inhibitor must be used, reduce pomalidomide dose by 50%.
- Dosage Adjustment for Patients with Severe Renal Impairment on Hemodialysis:
 - For patients with severe renal impairment requiring dialysis, the recommended starting dose is 3 mg daily (25% dose reduction). Take pomalidomide after completion of dialysis procedure on hemodialysis days.
- Dosage Adjustment for Patients with Hepatic Impairment:
 - For patients with mild or moderate hepatic impairment (Child-Pugh classes A or B), the recommended starting dose is 3 mg daily (25% dose reduction). For patients with severe hepatic impairment (Child-Pugh class C), the recommended dose is 2 mg (50% dose reduction).

Dexamethasone will be administered at a dose of 40 mg weekly. For subjects older than 75 years or underweight (body mass index [BMI] <18.5), the dexamethasone dose may be administered at a dose of 20 mg weekly. Dexamethasone may be reduced, if necessary, according to Table 10.

Table 10. Dose Modification Instructions for Dexamethasone Toxicities

| CTACAE Category | Toxicity | Dose Modification |
|------------------|--|---|
| Gastrointestinal | Grade 1-2 Dyspepsia, gastric or duodenal ulcer, gastritis requiring medical management | Treat with H2 blockers, sucralfate, or omeprazole. If symptoms persist despite above measure, decrease dexamethasone dose by 50%. |
| | ≥Grade 3 requiring hospitalization or surgery | Hold dexamethasone until symptoms adequately controlled. Restart at 50% of current dose along with concurrent therapy with H2 blockers, sucralfate or omeprazole. If symptoms persist despite above measure, discontinue dexamethasone and do not resume. |
| | Acute pancreatitis | Discontinue dexamethasone and do not resume |

PF-06863135
 C1071001
Final Protocol Amendment 9, 28 March 2023

Table 10. Dose Modification Instructions for Dexamethasone Toxicities

| CTCAE Category | Toxicity | Dose Modification |
|-----------------------|---|---|
| Cardiovascular | ≥ Grade 3 Edema limiting function and unresponsive to therapy or anasarca | Diuretics as needed and decrease dexamethasone dose by 25%; if edema persists despite above measures, decrease dose to 50% of initial dose; discontinue dexamethasone and do not resume if symptoms persist despite 50% reduction |
| Neurology/Psychiatric | ≥ Grade 2 interfering with function but not interfering with activities of daily living | Hold dexamethasone until symptoms adequately controlled. Restart at 50% of current dose. If symptoms persist despite above measure, discontinue dexamethasone and do not resume |
| Musculoskeletal | ≥ Grade 2 Muscle weakness Symptomatic and interfering with function but not interfering with activities of daily living | Decrease dexamethasone dose by 25%; if weakness persists despite above measures, decrease dose to 50% of initial dose; discontinue dexamethasone and do not resume if symptoms persist despite 50% |
| Metabolic | ≥ Grade 3 Hyperglycemia | Treatment with insulin or oral hypoglycemic agents as needed. If uncontrolled despite above measure, decrease dose by 25% decrements until levels are satisfactory |

